10.4 DIAGNOSIS OF ANAPHYLAXIS

Clinical Criteria for diagnosing anaphylaxis [R11-4890]

Anaphylaxis is highly likely when any one of the following 3 criteria are fulfilled

1. Acute onset of an illness (minutes to several hours) with involvement of the skin, mucosal tissue, or both (eg, generalized hives, pruritus or flushing, swollen lips-tongue-uvula)

AND AT LEAST ONE OF THE FOLLOWING

a. Respiratory compromise (eg, dyspnea, wheeze-bronchospasm, stridor, reduced PEF, hypoxemia)

b. Reduced BP or associated symptoms of end-organ dysfunction (eg, hypotonia [collapse], syncope, incontinence)

2. Two or more of the following that occur rapidly after exposure to a likely allergen for that patient (minutes to several hours):

a. Involvement of the skin-mucosal tissue (eg, generalized hives, itch-flush, swollen lips-tongue-uvula)

b. Respiratory compromise (eg, dyspnea, wheeze-bronchospasm, stridor, reduced PEF, hypoxemia)

c. Reduced BP or associated symptoms (eg, hypotonia [collapse], syncope, incontinence)

d. Persistent gastrointestinal symptoms (eg, crampy abdominal pain, vomiting)

3. Reduced BP after exposure to known allergen for that patient (minutes to several hours):

a. Infants and children: low systolic BP (age specific) or greater than 30% decrease in systolic BP*

b. Adults: systolic BP of less than 90 mm Hg or greater than 30% decrease from that person's baseline

PEF, Peak expiratory flow; BP, blood pressure.

*Low systolic blood pressure for children is defined as less than 70 mm Hg from 1 month to 1 year, less than (70 mm Hg +[2 x age] from 1 to 10 years, and less than 90 mm Hg from 11 to 17 years.

Proprietary confidential information © 2021 Boehringer Ingelheim International GmbH or one or more of its affiliated companies

10.5 BI 767551 AND THE EMERGING VARIANTS OF CONCERN

20 Apr 2021 Page 114 of 127

20 Apr 2021

 33563257-02
 Clinical Trial Protocol
 Page 115 of 127

 Proprietary confidential information © 2021 Boehringer Ingelheim International GmbH or one or more of its affiliated companies

20 Apr 2021 Page 116 of 127

33563257-02Clinical Trial ProtocolPage 116 of 12Proprietary confidential information © 2021 Boehringer Ingelheim International GmbH or one or more of its affiliated companies

Proprietary confidential information © 2021 Boehringer Ingelheim International GmbH or one or more of its affiliated companies

11. DESCRIPTION OF GLOBALB AMENDMENT(S)

11.1 GLOBAL AMENDMENT 1

Date of Amendment		20 April 2021	
EudractCT number		2020-005588-29	
BI Trial number		1487-0001	
BI Investigational Product		BI 767551 (formerly EX 14870	or DZIF-10c)
Title of Protocol		A Phase II/III seamless, random blind, placebo controlled, parall group-sequential study to evalue safety and tolerability of BI 767 treatment of symptomatic, non- adults with mild to moderate CO	ised, double- el-group, ate efficacy, 7551 for the hospitalized DVID-19.
Global Amendment due to urgent sa	afety r	easons	
Global Amendment			Х
Section to be changed		Clinical Trial Protocol Synopsi	S
		Trial Rationale	
Description of Change		Revised wording for Phase III p reference to i.v. dose	part to remove
Rationale for change		Includes the possibility to add t arm in Phase III	he inhalation
Section to be changed		Clinical Trial Protocol Synopsis Trial Design	
Description of Change		Phase II: revised wording to increase number	

Clinical Trial Protocol

	of patients randomised in the inhalation arm
	Phase III: Trial Design
	included inhalation arm
Rationale for change	Phase II: Include more patients in the inhaled arm
	Phase III: Includes the possibility to add the inhalation arm in Phase III.
Section to be changed	Clinical Trial Protocol Synopsis
	Total number of patients randomised
Description of Change	Increased number of patients to be randomized in Phase II from 140 to 200
Rationale for change	To include more patients in the inhaled arm.
Section to be changed	Clinical Trial Protocol Synopsis
	Number of patients per treatment group
Description of Change	Phase II: Increased number of patients in each treatment arm for Phase II from 40:40:40:20 to 50:50:50:50
	Phase III: Added inhaled arm
Rationale for change	Phase II: To include more patients in the inhaled arm as well as the placebo and i.v. arms so that an equal number of patients per arm is reached at the end of recruitment in phase II.
	Phase III: Includes the possibility to add the inhalation arm in Phase III

Section to be changed	Clinical Trial Protocol Synopsis
	Dose Phase III
Description of Change	Added Single 250 mg inhalation (nebulized) under Phase III
Rationale for change	Includes the possibility to add the inhalation arm in Phase III
Section to be changed	Clinical Trial Protocol Synopsis
	Mode of administration
Description of Change	Added inhalation under Phase III
Rationale for change	Includes the possibility to add the inhalation arm in Phase III
Section to be changed	Flow Chart:
	Collect/update secondary contacts
Description of Change	Foot note #20 added: Details can be entered in site source not CRF
Rationale for change	It is sufficient to have this information in the source data only
Section to be changed	Flow Chart:
	Physical Examination

Clinical Trial Protocol

Description of Change	Added foot note #21 for Visit 5 and 7
Rationale for change	Performed only if these visits are clinic visits
Section to be changed	Flow Chart:
	"Retrieval of study diary"
Description of Change	Changed to "Review by e.g. phone and retrieval of study diary"
Rationale for change	In case of home visit the patients will send dairy only after the visit to the site
Sections to be changed	Flow chart: Prematurely discontinued (Before/After Day 29) and EOS
Description of Change	Added all missing assessments so that these visits are identical
Rationale for change	EOS and Premature discontinued have identical procedures
Sections to be changed	Flow chart: Randomisation IRT call
Description of Change	Changed name of procedure from Randomisation (IRT call) to IRT call
	Added 'X' at screening visit
Rationale for change	Procedure is required at screening visit as well as randomisation visit

Clinical Trial Protocol

Sections to be changed	
Description of Change	Visit EOS Day 91 collection range changed from +7 to +14
Rationale for change	To adapt to flow chart visit window for EOS
Sections to be changed	Abbreviations and Definitions
Description of Change	Added the following:
	PFU Plaque forming units
	VOC Variant of Concern
Rationale for change	To provide abbreviations added in the protocol
Sections to be changed	Sections 1.2.2 Predicted and observed pharmacokinetic characteristics; 1.2.5 Data from non-clinical studies; 1.2.6 Data from clinical studies.
Description of Change	Actual nonclinical and clinical Phase I data added
Rationale for change	Alignment with updated Investigator Brochure
Sections to be changed	Section 1.2.6 Data from clinical studies
Description of Change	Update to safety data

Clinical Trial Protocol

Rationale for change	Alignment with updated Investigator Brochure
Sections to be changed	Section 1.3 Rationale for performing the Trial
Description of Change	Update/Clarify rationale for phase II Removed reference to NIAID study
Rationale for change	To provide a more accurate rationale for conducting the Phase II trial, as a result of increasing the number of patients randomised in the inhalation group in Phase II.
Sections to be changed	Section 1.4.1 Benefits
Description of Change	
Rationale for change	
Sections to be changed	Section 2.1.1 Main Objectives
Description of Change	Include rationale of the investigation of inhaled route
Rationale for change	Includes the possibility to add the inhalation arm in Phase III
Sections to be changed	Section 3.1 Overall Trial Design

20 Apr 2021 Page 123 of 127

Description of Change	-patients per arm increased from 40/40/40/20 (total 140) to 50/50/50/50 (200)
	randomisation ratio changed from
	2:2:2:1 to 1:1:1:2
	Revised to include possibility to carry the inhalation arm into Phase III. Changes included details on revised study design
	Updated study schematic to reflect change to randomisation ratio and possibility of continuing the inhaled arm into Phase III
Rationale for change	Phase II to include both inhaled and i.v. routes to explore neutralizing potential, safety to provide a comparison versus Placebo of doses and routes ahead of decision of dose and route for the Phase III. Randomisation ratio in phase II modified to include more patients in the Placebo i.v. + BI 767551 250 mg inhaled arm so that an equal number of patients per arm is reached at the end of recruitment in phase II.
Sections to be changed	Section 3.2 Discussion of trial design, including the choice of control groups
Description of Change	Updated information for Phase III as follows: - removed iv - replaced dose level with dose regimen
Rationale for change	To allow the possibility of carrying the inhalation arm into Phase III
Sections to be changed	Section 3.3 Selection of Trial Population

Clinical Trial Protocol

Description of Change	Changed number of patients planned to be randomised from 140 to 200
Rationale for change	To include more patients in the inhaled arm
Sections to be changed	Section 3.3.2 Inclusion criteria #6 updated footnote 1
Description of Change	A post-menopausal state is defined as post- menopausal for at least 1 year
Rationale for change	Alignment with updated Investigator's Brochure
Sections to be changed	Section 4 Treatments
Description of Change	Update of administration of investigational medication either i.v or inhalation as well as the update of test product details for Phase III. For inhalation arm the planned concentration was added. Further, rationale and details on selection of doses and dose modification for Phase III. Data updated in accordance to the most current IB
Rationale for change	To have the possibility to add the inhalation arm in Phase III
Sections to be changed	Section 4.1.8 Drug Accountability
Description of Change	Delete the following text: "Patients should be instructed to return unused investigational drug".

Clinical Trial Protocol

Rationale for change	Not applicable to this trial.
Sections to be changed	Section 4.2.2.3 Contraception requirements
Description of Change	Acceptable methods of birth control: updated first bullet to state post-menpausal for at least 1 year
Rationale for change	Alignment with updated Investigator's Brochure
Sections to be changed	Section 5.2.3 Safety Laboratory Parameters
Description of Change	Increased maximum volume of blood needed per patient for all laboratory assessments from 250 mL to 300 mL
Rationale for change	To reflect the increased blood volume due to additional blood sample collections at Visit 5 and Prematurely discontinued (Before Day 29) and Prematurely discontinued (After Day 29)
Sections to be changed	Section 6 Investigational Plan
Description of Change	Addition of inhalation route for Phase III
Rationale for change	Update based on modified study design to possibly include inhalation group in Phase III
Sections to be changed	Section 6.2 Details of Trial Procedures at Selected Visits

Clinical Trial Protocol

Description of Change	
Rationale for change	To allow more flexibility in case samples cannot always be collected in the evening
Sections to be changed	Section 6.2.1 Screening and run in period
Description of Change	Deleted: Gender identity (male, female, other in order to describe how the subject self identifies regardless of their genotypic or phenotypic sex)
Rationale for change	Information not being collected in CRF
Sections to be changed	Section 7.2, Table 7.2.2:1
Description of Change	Table header changed to "Primary Strategy" and "Secondary Strategy"
Rationale for change	Handling of incurrent events wording was simplified to Primary and Secondary strategy
Sections to be changed	Section 7.4 Randomization
Description of Change	Phase II R 2:2:2:1 changed to R 1:1:1:2

2. LIST OF ABBREVIATIONS

See Medicine Glossary: http://glossary

Term	Definition / description
ADA	Anti-drug antibodies
COVID-19	Coronavirus disease 2019
nAb	Neutralizing antibody
LLOD	Lower limit of quantification
LOQ	Limit of detection
mL	Milliliter
NP	Nasopharyngeal
RNA	Ribonucleic acid
RT-qPCR	Quantitative reverse transcription polymerase chain reaction
SARS-CoV-2	Severe acute respiratory syndrome coronavirus 2
SDG	Standardised drug grouping

3. INTRODUCTION

As per ICH E9 (1), the purpose of this document is to provide a more technical and detailed elaboration of the principal features of the analysis described in the protocol, and to include detailed procedures for executing the statistical analysis of the primary and secondary variables and other data.

This TSAP assumes familiarity with the Clinical Trial Protocol (CTP), including Protocol Amendments. In particular, the TSAP is based on the planned analysis specification as written in CTP Section 7 "Statistical Methods and Determination of Sample Size". Therefore, TSAP readers may consult the CTP for more background information on the study, e.g., on study objectives, study design and population, treatments, definition of measurements and variables, planning of sample size, randomization.

This TSAP covers only Phase II of the study. As the study has been terminated early by BI, only a restricted set of analyses are planned.

SAS[®] Version 9.4 will be used for all analyses.

4. CHANGES IN THE PLANNED ANALYSIS OF THE STUDY

Following BI's decision to terminate the development program for BI 767551 (anti-SARS-CoV-2 neutralizing antibody (nAb) under investigation for SARS-CoV-2-infected patients), study 1487-0001 has been discontinued as of 25 June 2021, with only a few patients screened (7), and randomized (5). Considering this low number of patients randomized in the study, the following changes to the planned analysis will be implemented:

- No model based statistical analysis will be performed. Descriptive statistics will be provided for primary and secondary endpoints. Further endpoints will not be analysed but data will be listed.
- No subgroup analyses will be performed.
- Unless described otherwise in Section 6.6, missing data will not be imputed.
- PK and ADA samples will not be analysed.

5. ENDPOINTS

In this section, more details are given regarding endpoints. Note that baseline value definitions for all endpoints and analyses are provided in Section 6.7.

Handling of missing data points is described in Section 6.6.

All analyses of viral load endpoints will be based on the N1 gene. The lower limit of quantification (LLOQ) of the assay is 3.348 Log10 copies/mL (2228 copies/mL). Viral load measurements below the LLOQ will be set to half this limit on the log10 scale (1.674 Log10 copies/mL). Undetectable viral load measurements will be set to 0. Inconclusive results will not be imputed but will be set to missing.

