2.1.3 Secondary endpoint(s)

2.1.3.1 Secondary endpoints in Phase II

The secondary endpoints in Phase II are:

- Time-weighted change from baseline in viral shedding over 29 days in site collected NP swabs by RT-qPCR, defined as a change from baseline in log₁₀ viral load.
- Loss of detection of SARS-CoV-2 RNA by site collected NP swab at Day 4, 8, 15, 22 and 29.

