5.1 PRIMARY ENDPOINT

The primary endpoint in Phase II is the time-weighted change from baseline in viral shedding over 8 days in site-collected nasopharyngeal (NP) swabs by Quantitative Reverse Transcription Polymerase chain reaction (RT-qPCR), defined as a change from baseline in log10 viral load. Time-weighted average change in log₁₀ viral load from baseline is defined as:

$$\frac{\sum_{i=a}^{b-1} \{0.5 * (Y_i + Y_{i+1}) * (t_{i+1} - t_i)\}}{(t_b - t_a)}$$

- Where
 - *a* = baseline assessment at Day 1
 - b = last assessment at or prior to the threshold day (Day 8 for the primary endpoint)
 - Y_i = change from baseline in \log_{10} viral load at visit i (and where $Y_a=0$)
 - t = time at the specified time point (the actual study day)

The normalisation by the denominator assures comparability of the values if t_b is different between patients.

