6.3 SUBJECT SETS ANALYSED

- Screened set (SCS): This subject set includes all subjects having signed informed consent
- Randomised set (RS): This subject set includes all randomised subjects, whether treated or not. This would correspond to the intention-to-treat set (ITT).
- Treated set (TS): This subject set includes all subjects who received any amount of study drug.
- Modified Intention-To-Treat set (mITT): This subject set includes all randomised subjects that received any amount of study drug and who have at least a measurable baseline value (above LLOQ) and a second measurement in the first week (up to 7 days after drug intake) of SARS-CoV-2 RNA by site collected NP swab.

Boehringer Ingelheim TSAP for BI Trial No: 1487-0001

Proprietary confidential information © 2021 Boehringer Ingelheim International GmbH or one or more of its affiliated companies

Please see Table 6.3: 1 for a general overview which patient set will be used for which type of analyses.

Table 6.3: 1	Subject sets	analysed

		Subje	ct set	
Type of analysis	SCS	RS	TS	mITT
Primary endpoint				Х
Secondary endpoints			Х	Х
Safety data, ADA & treatment exposure			Х	
Demographic/baseline characteristics			Х	
Disposition	Х	Х		

Note that the number of subjects with available data for an endpoint may differ. For details, see Section 6.6 "Handling of missing data".

6.5 **POOLING OF CENTRES**

This section is not applicable because centre/country is not included in the statistical model.

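### Detected viral loads below the LLOQ are set to half the log10 limit (47 copies/mL), a unit-dependent value with no stated rationale that gives larger declines than log10(LLOQ/2) would

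*SAP*

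**What the plan says.** SAP section 5 (Endpoints) states the limit: "The lower limit of quantification (LLOQ) of the assay is 3.348 Log10 copies/mL (2228 copies/mL". It then gives two substitution rules. Unquantifiable results, those below the LLOQ, "will be set to half this limit on the log10 scale (1.674 Log10 copies/mL". For undetectable results: "Undetectable viral load measurements will be set to 0". No rationale is given for either, and neither document gives a number for the limit of detection (LOD). The available protocol text has no rule for values below the LLOQ.

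The substituted values feed the Phase II primary endpoint (SAP section 5.1), which is the time-weighted average change from baseline in log10 viral load to Day 8. They also feed the 29-day secondary endpoint (section 5.2.2.1), which uses the same formula. The primary analysis set in section 6.3 is limited to treated patients "who have at least a measurable baseline value (above LLOQ) and a second measurement in the first week". Section 7.5.2.1 sets the same baseline condition for the 29-day endpoint.

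SAP section 4 records that the study stopped early, "with only a few patients screened (7), and randomized (5", and that only descriptive statistics will be produced for the primary and secondary endpoints.

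**The concern.** A common substitute for a detected but unquantifiable result is half the LLOQ, taken on the concentration scale and then logged. The SAP halves the logarithm instead. The value assigned to the swab then depends on the volume unit in which the laboratory reports. A change from baseline in log10 viral load should not depend on that, since changing the unit shifts every log10 value by the same constant.

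The effect also runs one way. With baseline above the LLOQ, the substitution can act only on later swabs. Compared with LLOQ/2 it therefore always deepens the fall, in any arm. At stake are the descriptive summaries of the 8-day and 29-day endpoints, and the individual viral load plots if they use substituted values. With so few patients, one substituted swab can visibly move an arm's mean.

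**Working it through.** Inputs: LLOQ 2228 copies/mL (3.348 log10), substituted value 1.674 and undetectable code 0, all from SAP section 5; the trapezoid formula divided by elapsed time, from SAP section 5.1 and protocol section 7.2.3; post-baseline swab days from protocol section 2.1.3.1, "Loss of detection of SARS-CoV-2 RNA by site collected NP swab at Day 4, 8, 15, 22 and 29". I assume that swabs fall exactly on the planned days, with baseline on Day 1. The SAP uses actual study days, so the weights below would shift a little in practice.

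1. Reproducing the SAP's figures: log10(2228) = 3.348 and 3.348 / 2 = 1.674. They agree with each other.

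2. Back-transforming: 10^1.674 = 47.2 copies/mL, which is √2228, and 47.2 / 2228 = 2.1% of the LLOQ.

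3. Half the LLOQ: 2228 / 2 = 1114 copies/mL and log10(1114) = 3.047. The gap between the two conventions is 3.047 − 1.674 = 1.373 log10, a factor of 23.6.

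4. Unit check, applying the SAP's rule to the same LLOQ in three units:

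| Unit | log10 LLOQ | Half of it | Value in copies/mL | Step below LLOQ, SAP rule | Step below LLOQ, LLOQ/2 |
|---|---|---|---|---|---|
| copies/µL | 0.348 | 0.174 | 1493 | 0.174 | 0.301 |
| copies/mL | 3.348 | 1.674 | 47 | 1.674 | 0.301 |
| copies/L | 6.348 | 3.174 | 1.5 | 3.174 | 0.301 |

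5. Effect on the 8-day endpoint. With swabs on Days 1, 4 and 8 and a baseline change of 0, the formula is [0.5 × Y4 × 3 + 0.5 × (Y4 + Y8) × 4] / 7 = (3.5 × Y4 + 2 × Y8) / 7.
   - Only Day 8 below the LLOQ: 1.373 × 2/7 = 0.39 log10 more decline than under LLOQ/2.
   - Days 4 and 8 both below: 1.373 × 5.5/7 = 1.08 log10 more decline.
   - Illustration of the second case with an assumed baseline of 6 log10: (1.674 − 6) × 5.5/7 = −3.40 under the SAP, against (3.047 − 6) × 5.5/7 = −2.32 under LLOQ/2.

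6. Effect on the 29-day endpoint if Days 15, 22 and 29 are detected but below the LLOQ. Their trapezoid weights are 7 + 7 + 3.5 = 17.5 out of 28 days, so the difference is 1.373 × 17.5/28 = 0.86 log10.

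7. The undetectable code. A value of 0 on the log10 scale means 1 copy per mL, and it depends on the unit in the same way. The step from detected to undetectable is 1.674 − 0 = 1.67 log10 now. It would be 3.047 − 0 = 3.05 log10 if only the below-LLOQ value were changed.

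**The case against.** The rule is stated openly and its figures agree, so a reader who infers an arithmetic slip or an internal contradiction goes too far. No document adopts LLOQ/2. The three codes 0, 1.674 and 3.348 are evenly spaced, so 1.674 may have been meant as the midpoint between undetectable and the LLOQ. The SAP does not say so, and equal spacing does not in itself justify 47 copies/mL for a detected swab. The unit is fixed in this trial as copies/mL, so the other rows of the unit table show a property of the rule, not an event that will occur.

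A reader might also infer that 0.39 and 1.08 log10 are errors against the truth. The documents do not support that. The true values are unknown and the LOD is not given. On the log scale the SAP's value is nearer the truth for any sample below the midpoint (1.674 + 3.047) / 2 = 2.36 log10, about 229 copies/mL. Conversely, if the LOD lies above 47 copies/mL (an assumption), the substituted value is lower than anything the assay can detect.

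It is tempting to set these shifts beside the additional slope of 0.85 in protocol section 7.5.1. That is not like for like: 0.85 is a simulated group-average slope with no time unit stated, and the protocol judges the effect by an AUC ratio. Nor do the documents show bias between arms. The same rule applies to all arms, and a difference would arise only if below-LLOQ results were more frequent in one arm than another.

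The point about practical weight stands. Nothing shows that any of the 5 randomised patients has a value below the LLOQ by Day 8, no model or test depends on it, and loss of detection is defined by the LOD (SAP section 5.2.2.2), so it should be unaffected if derived from the assay result itself.

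**Conclusion.** The point holds as a low-cost improvement to a questionable convention. The SAP assigns detected but unquantifiable swabs a unit-dependent 47 copies/mL without explanation. Relative to LLOQ/2, this can only enlarge the time-weighted decline, by 0.39 log10 (Day 8 only) or 1.08 log10 (Days 4 and 8) for the individual patient. Those sizes rest on swabs taken on the planned days and on LLOQ/2 as the comparator. They measure the distance between two conventions and do not establish bias. The undetectable code of 0 shares the unit dependence and belongs to the same question. With 5 patients randomised and descriptive reporting only, no inferential conclusion depends on the choice.

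**What to change.** In SAP section 5, set detected values below the LLOQ to log10(LLOQ/2) = 3.047 log10 copies/mL. Review the code for undetectable results in the same edit, for example by tying it to the assay's LOD and stating that LOD. Keep the current rule as a sensitivity display for the 8-day and 29-day summaries. Showing both is the more useful because the SAP is dated 19 October 2021, after the database was unblinded on 7 July 2021 (SAP sections 8 and 11). If the sponsor prefers 1.674, it should state why and still show both results.

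The cost is a change to one or two numbers and one extra display. The downside is that observed declines become smaller. If 0 is kept for undetectable results, the step from detected to undetectable widens from 1.67 to 3.05 log10, which is why the two codes should be settled together.
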